[name]	Investigator / Operational Change Manager	NHS Blood and Transplant [name]	[contact] [contact]
[name]	Investigator / Head of Donation Technology	NHS Blood and Transplant [name]	[contact] [contact]
[name]	Investigator / Donor Consultant	NHS Blood and Transplant [name]	[contact] [contact] [contact] [name] PA to SB [contact] [contact]
[name]	Investigator / Scientific Study Coordinator	DPHPC University of Cambridge [name]	[contact] [contact] [contact]
[name]	Investigator / Scientific Study Coordinator	NHSBT Cambridge Centre [name]	[contact] [contact] [contact]
[name]	Investigator / Chief Information Officer	DPHPC University of Cambridge [name]	[contact] [contact] [contact]
[name]	Investigator / Statistician	DPHPC University of Cambridge [name]	[contact] [contact] [contact]
[name]	Investigator / Director NIHR Cambridge Biomedical Research Centre	Department of Medicine University of Cambridge School of Clinical Medicine Addenbrookes Hospital [name]	[contact] [contact]
[name]	Investigator /	Cambridge University	[contact]

	Associate Director NIHR BioResource	Hospital NHS Foundation Trust, [name]	Mob: [name] [contact] [name] PA to NK [contact] [contact]
Project administration			
Name		Affiliation	Contact details
COMPARE Study Helpdesk [name] [name] [name] [name]		DPHPC University of Cambridge [name]	[contact] [contact] www.compare.org.uk

1. Protocol Summary

Title:	Comparison of NHSBT's current approach with three alternative strategies to assess haemoglobin levels in whole blood donors (COMPARE Study)
Short title:	COMPARE
Sponsor name & reference:	NHS Blood and Transplant
Funder name & reference	NHS Blood and Transplant and National Institute of Health Research
ISRCTN no:	90871183
Design	Multi-site observational study in blood donors in England.
Overall aim:	
To evaluate the optimum method to measure haemoglobin levels in potential whole blood donors in advance of each donation in NHSBT's high-throughput context.
 
A further aim is to establish a bioresource of healthy volunteers using samples and data collected during the study to be used in future approved research projects looking at donor and public health. In the future, comparisons to other bioresources related to people with common and rare diseases may also shed light on the causes of diseases.

Primary endpoint:	The primary endpoint will be the proportion of donors in the study who would have been inappropriately bled by each method (ie, the proportion of donors for whom a given method would not identify as having sub-threshold haemoglobin levels [ie, <125g/L for women and <135g/L for men] as measured by a Sysmex haematology analyser).
Secondary endpoints:	
 1) Differences in the proportion of donors who would have been inappropriately bled when comparing the various newer methods to be studied with one another 2) Differences in the proportion of donors who would have been inappropriately bled when comparing the two non-invasive devices to be studied with each other 3) Feasibility and acceptability of different methods, according to the views of and blood services staff 4) Cost-effectiveness of different methods 5) Variability of the performance of different methods by donors' personal characteristics. 6) Medium and long-term health consequences of inappropriately bleeding at donation. 7) Biological mechanisms of whole blood donation on iron kinetics, iron absorption and iron incorporation in erythrocytes in donors who have particular genetic profiles.
Inclusion & exclusion criteria:	
Inclusion criteria:
 
 1) age ≥18 years and fulfilling all normal criteria for blood donation with the exception of pre-donation haemoglobin

	
levels measured using the current NHSBT methods; 2) willing to undergo additional haemoglobin measurement; 3) willing to donate an extra blood sample to be i) used for measurement of haemoglobin using an automated cell counter and ii) stored for future research 4) willing to come back for a subsequent appointment at standard donation interval (ie 12-wk and 16-wk for men and women respectively) – only relevant for the 18,000 participants to be enrolled in the first stage of recruitment.
 
Exclusion criteria: 1) participants who do not have internet access and/or are not willing to provide an email address for study correspondence (as the study will aim to be almost “paper-less” and will involve remote web-based data collection);

Planned number of sites:	10 mobile teams across England.
Summary of haemoglobin measurements:	
Haemoglobin levels will be measured using three alternative methods:
 
1) a “post-donation” method: This method involves using haemoglobin levels obtained from a “gold standard” haematology analyser at the most recent blood donation visit to predict the donor’s haemoglobin level at the next visit (ie, typically 12-16 weeks later)
 
2) a capillary point-of-care test: This method involves taking a drop of capillary blood after a finger-prick and measuring haemoglobin levels using a rapid Hemocue® test.
 
3) a non-invasive strategy: This method involves either of two hand-held spectrometer devices that estimate haemoglobin levels by shining a light on the skin of a donor’s finger.

Duration of recruitment:	Approximately 37 weeks
Translational component	The results from this study will inform national policies that should optimise current haemoglobin screening approach in blood donors across England.
Other related research	Added value will be provided by this study’s creation of a bio-resource that will, with separate future funding, enable detailed study of the health of blood donors. More generally, this study should encourage future NHS Blood and Transplant studies that address other relevant service needs.

Table of Contents

1 Abbreviations	1
2 Amendment history.....	2
3 Introduction	3
3.1 Background.....	3
3.2 Objectives	4
3.2.1 Primary objective	4
3.2.2 Secondary objective	4
4 Study design.....	5
4.1 Haemoglobin strategies to be compared	5
4.2 Sampling framework	5
4.3 Primary and secondary endpoints	6
4.3.1 Primary endpoint	6
4.3.2 Secondary endpoint.....	7
4.4 Study sites	7

15.3	No further use	30
15.4	Positive microbiology	30
15.5	Recording withdrawals	30
16	Sample size.....	3
16.1	Sample size	31
16.2	Statistical analysis plan	31
17	Finance and insurance arrangements	33
17.1	Finance	33
17.2	Insurance	33
18	Publication policy.....	33

1. Abbreviations

AE	Adverse event
AED	Adverse event of donation
NHSBT	NHS Blood and Transplant
DHC	Donor health check form
DIN	Donation identification number
MHRA	Medicines and healthcare regulatory agency
NCC	National call centre
NIHR	National institute for health research
REC	Research ethics committee
SAE	Serious adverse event
SAED	Serious adverse event of donation
SMG	Study management group
SSC	Study steering committee
UoC	University of Cambridge

2. Amendment history

Amendment No.	Protocol version No.	Date issued	Author(s) of document / changes	Details of changes made
*	1	13/08/15	[name]	
	2	12/11/15	[name]	Additional details on blood sample processing and analysis and future use of stored samples (see Section 13)
	3	01/12/15	[name]	The creation of a BioResource has been included as an aim of the study in Sections 1, 3.2.1, and 4.3.2. Additional details have been added on the use of samples / data for approved research studies in Section 13.1
	4	17/12/15	[name]	
 1. New and updated versions of participant documents have been incorporated in the text and annexes. 2. ISRCTN and study sponsor reference number added (front cover and Section 1: Protocol summary) 3. Details of study sites have been added (see Section 4.4.) 4. Details of collection of an additional 3ml blood in TEMPUS tube (Sections 9.1.3, 10.4, 13, 13.1).
	5	01/07/2016	[name]	
 1. Addition of questionnaire reminders (partial and non-responders) for Stage 1 participants who have attended two donation sessions and have not completed the baseline questionnaire 2. Removal of the Stage 2 donor copy consent form at the screening booth

* List details of all protocol amendments here whenever a new version of the protocol is produced

3. Introduction

3.1 Background

What is the unmet need? Blood services are mandated to measure the haemoglobin concentration of potential whole blood donors in advance of each donation, both to protect the health of donors (ie, to prevent collection from anaemic donors) and to ensure the quality of blood products. The European legislation on selection criteria of blood donors states that haemoglobin levels should be $\geq 125\text{g/L}$ for women and $\geq 135\text{g/L}$ for men to allow blood donation. However, despite such legislation, even within Europe national blood services use varying haemoglobin screening approaches (**Table 1**). This situation reflects a lack of rigorous evidence to support a single optimal policy.

NHS Blood and Transplant (NHSBT) currently use a “copper sulphate finger prick test” on capillary blood to measure pre-donation haemoglobin level, and if this test indicates that the haemoglobin levels are low, donors are asked to provide a sample of venous blood for further testing using the more precise “Hemocue®” test. However, this method has limitations. In an analysis of data from 45,000 donors who gave blood in England during 2012-14, we found that almost 10% were judged to have been inappropriately bled (ie, they had haemoglobin levels below the EU directive cut-off points) when the current NHSBT approach was compared against the “gold standard” haematology analyser.

Table 1. Haemoglobin screening strategies in selected blood services

Organisation	Strategy	Screening procedure		
		Device	Method	Sample
NHSBT*	pre-donation	CuSO ₄ ± Hemocue	gravimetric/photometry	capillary/venous
Bavarian Red Cross	pre-donation	MBR Haemospect	reflection spectroscopy	non-invasive
Irish Blood Transfusion Service	pre-donation	MBR Haemospect	reflection spectroscopy	non-invasive
Orsola-Malpighi Hospital, Bologna (Italy)	pre-donation	Orsense NMB200	occlusion spectroscopy	non-invasive
Blood Donors in Denmark*	post-donation	Cell counter	spectrophotometry	venous
Etablissement Francais du Sang *	post-donation	Cell counter	spectrophotometry	venous
German Hospital Transfusion Centres **	post-donation	Cell counter	spectrophotometry	venous
Australian Red Cross	pre-donation	Hemocue	photometry	capillary
Canadian Blood Services	pre-donation	DiaSpect	photometry	capillary

*first time donors presenting for a donation undergo a pre-donation screening test using a portable photometer (Hemocue/CompoLab)

**Department of Transfusion Medicine, Eberhard Karls University Tuebingen; Department of Transfusion Medicine, Westfaelische Wilhelms University Muenster; University Medical Centre Schleswig-Holstein.

There are about 1.3 million blood donors each year in England who provide a total of 1.9 million donations. Given NHSBT's duty of care to such a large group of volunteers, there is a fundamental need to determine the optimum method to measure haemoglobin concentration in advance of each donation in order to reduce the number of donors inappropriately bled. An important objective of NHSBT, and a major motivator of the current proposal, is also to move towards a more donor-friendly approach to measure haemoglobin level.

What are the alternatives strategies for haemoglobin measurement? Several national blood services in Western countries use a spectrophotometric test (Hemocue®) on capillary blood obtained by a finger-prick. However, in recent years, alternative approaches to haemoglobin screening have been adopted by blood services in major European countries because of their potential to provide more accurate tests, a more donor-friendly way of testing that saves time at donation sessions, and a reduction in hazardous material for

disposal. Two of the most promising approaches are the use of: (1) a “post-donation” method (this method involves using haemoglobin levels obtained from a “gold standard” haematology analyser at the most recent blood donation visit to predict the donor’s haemoglobin level at the next visit); and (2) a non-invasive strategy (this method involves either of two hand-held spectrometer devices that estimate haemoglobin levels by shining a light on the skin of a donor’s finger). However, the comparative merits of these approaches remain uncertain, as they have been introduced into practice without rigorous scientific evaluation.

Will other studies provide the necessary evidence? To our knowledge, there are no previous (or planned) studies in the UK or elsewhere that aim to compare different strategies to measure haemoglobin levels in blood donors.

3.2 Objectives

3.2.1 Primary objective

The main objective of this study is to provide a robust comparison of the three alternative strategies for haemoglobin testing (ie, a “post-donation” method, capillary blood Hemocue®, and non-invasive spectrometry), comparing each with NHSBT’s current approach and with a “gold standard” haematology analyser. The study’s principal outcome will be the proportion of donors that would have been inappropriately bled with each method.

A further objective is to establish a bioresource of healthy volunteers using samples and data collected during the study to be used in future approved research projects looking at donor and public health. In the future, comparisons to other bioresources related to people with common and rare diseases may also shed light on the causes of diseases.

3.2.2 Secondary objective

Secondary key outcomes will include feasibility and acceptability of the methods for donors and NHSBT staff, cost-effectiveness, and performance of tests in donor subpopulations (ie, study of whether results for different methods vary importantly by age, sex, ethnicity, genetic make-up etc).

4. Study design

4.1 Haemoglobin strategies to be compared

We will compare the following three haemoglobin strategies that are used by various blood services in major Western industrialised countries against the results of a “gold standard” haematology analyser and against the results of the current NHSBT method:

1) a “post-donation” method: This method involves using haemoglobin levels obtained from a “gold standard” haematology analyser at the most recent blood donation visit to predict the donor’s haemoglobin level at the next visit (ie, typically 12-16 weeks later)

2) a capillary point-of-care test: This method involves taking a drop of capillary blood after a finger-prick (ie, the same finger-prick used for NHSBT’s routine copper sulphate test) and measuring haemoglobin levels using a rapid Hemocue® test. (NB: The point-of-care Hemocue test involves capillary blood, whereas the Hemocue® test currently used by NHSBT involves a venous blood sample). Hemocue® (HemoCue AB, Ängelholm, Sweden) is a point-of-care device tested according to IEC 61010-1 that complies with IVD Medical Device Directive 98/79/EC.

3) a non-invasive strategy: This method involves either of two hand-held spectrometer devices (ie, MBR Haemospect® versus Orsense NMB200®) that estimate haemoglobin levels by shining a light on the skin of a donor’s finger.

The MBR Haemospect® device (produced by MBR Optical Systems GmbH & Co. KG), is a hand-held, point-of-care test that uses transcutaneous reflection spectroscopy to measure haemoglobin level. The device was CE marked in 2008. Using a small probe head directly placed on the finger, the device shines light onto the skin and underlying tissues, then measures the wavelength of the light reflected back. No safety concerns have been reported and it is currently used in the Irish Blood Transfusion Service. The Orsense NMB200® device (produced by OrSense Ltd) is a hand-held, point-of-care test that uses a non-invasive occlusion spectroscopy method to measure haemoglobin level. The device was CE marked in 2009. The device is composed of a ring-shaped sensor probe that fits on the donor’s finger, and a portable desktop monitor that calculates and displays the measurement result. No safety concerns have been reported and it is currently used in some transfusion services in Italy.

4.2 Sampling framework

Over a period of about 37 weeks, we will enrol about 31,000 whole blood donors in England. The donors will derive from at least 10 NHSBT “mobile” blood donation teams that operate on a regular basis at the same locations. We estimate that about 120 whole blood donors will attend each of these sessions daily. Assuming 25% of donors at these centres agree to participate in this study (an expectation based on prior experience), we anticipate recruitment of 30 donors / day per mobile centre (ie, a total of 300 participants / day across the 10 centres). Hence, we estimate the recruitment of 1,500 participants / week, assuming recruitment 5 days per week. In the event of slower-than-anticipated recruitment, we plan to extend the duration of the recruitment and/or involve >10 mobile donation teams.

[figure not shown]
The study will involve two stages of recruitment (**Figure 1**).

Stage 1: will involve head-to-head comparison in a common set of about 12,500 participants of the three new methods (described above) and NHSBT’s current method for haemoglobin testing (copper sulphate test with or without venous Hemocue®). Samples will also be sent for testing on the “gold standard” haematology analyser to support the “post-donation” strategy.

The post-donation method requires Stage 1 participants to attend two successive blood donation visits. At the first visit, participants will consent and provide a research sample for testing on the “gold standard” haematology analyser. Prior to donating at this visit, participants’ haemoglobin levels will be tested via NHSBT’s routine methods only. At the second visit participants will receive measurements of their haemoglobin levels via standard NHSBT methods and also by i) capillary point of care Hemocue® and ii) one of the two non-invasive tests (ie, either MBR Haemospect® or Orsense NBM200®). In addition a sample collected at this 2nd visit will be sent for testing on the “Gold Standard” haematology analyser). We will enrol about 18,000 donors at the first visit in order to yield an anticipated 12,500 participants who attend two successive visits, assuming a non-attendance rate of 30% at the second visit.

Stage 2: One of the new methods to be evaluated (ie, non-invasive spectrometry) involves a choice between two commercially-available devices. It would be ideal to conduct a head-to-head comparison of these two devices in the same set of participants as the other methods are to be compared in. Unfortunately such an approach would likely be too time-consuming and disruptive to NHSBT’s high-throughput service. Hence, we plan a second stage of recruitment that will involve enrolment of a further approximately 13,000 participants, focusing on the comparison of two different non-invasive spectrometry devices. During the second stage of recruitment, selection of mobile donation centres will be done in a way to over-sample donors of non-European ancestry (eg, those of African, Middle Eastern, and South Asian ancestry). The rationale is that the performance of non-invasive spectrometry devices is known to differ in people with different skin colour and tone.

Figure 1: Study design

^a assuming ~30% drop-out rate 18,000 donors need to be recruited at the previous donation visit.

4.3 Primary and secondary endpoints

4.3.1 Primary endpoint

The primary endpoint will be the proportion of donors in the study who would have been inappropriately bled by each method, ie, the proportion of donors for whom a given method would not identify as having sub-threshold haemoglobin levels [ie, <125g/L for women and <135g/L for men] as measured by a “gold standard” haematology analyser. The principal assessment will compare the current NHSBT screening method with each of the three other

alternative methods (ie, three pair-wise comparisons). We hypothesise that the current NHSBT method will involve a higher proportion of donors inappropriately bled than the other newer methods. The null hypothesis is that there are no differences across methods in the numbers of donors who would have been inappropriately bled.

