7.6. Set up of COMPARE study helpdesk

A COMPARE study helpdesk will be established at the academic coordinating centre, at the University of Cambridge (UoC), prior to the start-up of the study. A training programme will be delivered to the helpdesk which will cover all aspects of the team's responsibilities during the study, which will be to:

1. Deal with donor queries regarding their participation in the study.
2. Deal with and action donor requests to withdraw from the study.
3. Deal with queries from UoC regarding non-reconciliation of consent forms or samples to donors registered on the study.

8. Summary of study procedures

A summary of study procedures is show in **Table 2** below.

Table 2: Study procedures in Stage 1 and Stage 2 participants (at-and post-session)

Study Procedures	Stage 1				Stage 2	
	Head-to-head comparison of 3 new methods and NHSBT's current method for Hb testing. One of the new methods - the post-donation method - requires participants to attend two successive blood donation visits.					
	Visit 1		Visit 2			
	At session	Post-session	At session	Post-session	At session	Post-session
Invitation & consent	●				●	
Hb screening (per participant)						
Standard NHSBT	●		●		●	
Post donation ^a	●		●			
Capillary Hemocue®			●			
Non-invasive (one of two)			●		●	
Research samples^b	●		●		●	
Health / lifestyle questionnaire		●				●
Hb screening questionnaire				●		●

^a This method requires Hb measurement using "glod standard" haematology analyser.

^b Research samples include 4ml EDTA, 6ml EDTA and 6ml serum tubes The 4ml EDTA will be used to perform Full Blood Count on "Gold Standard" haematology analyser.

9. Stage 1 study procedures

9.1 Donation visit 1

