9.2.3 Donor screening

The screening donor carer collects the study-specific wallet from the welcome desk and checks the DHC for a temporary message.

If the DHC has a temporary message, indicating that a research sample should be taken, the donor carer will:

1. Conduct pre-donation medical screening; if a participant is deferred for reasons other than for low haemoglobin, they will not provide any samples or measurements for the research and their participation in the study will end here
2. Perform a copper sulphate finger prick test (with or without a subsequent venous sample for HemoCue®) in those donors who pass the pre-donation medical screening
3. Perform a haemoglobin measurement on a capillary sample with the HemoCue®. This will be performed at the same time as the copper sulphate test to avoid additional finger pricks
4. Perform a haemoglobin measurement using a non-invasive device (i.e. either the Haemospect® or Orsense NMB200®, whichever is in current use by the mobile team)
5. Collect a research sample if the participant fails the copper sulphate test (if the participant passes the copper sulphate test, the donor will provide the research samples at the donation bed as part of their normal blood donation).

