16.1 Sample size

The overall study sample size has been determined on the basis of the following (partially overlapping) considerations: (i) the need to generate evidence sufficiently compelling to influence regulators and policy-makers; (ii) NHSBT's duty of care to 1.3 million blood donors per year, making it vital for the service to evaluate even subtle changes in the proportion of donors that are bleed with an haemoglobin levels below the recommended threshold; (iii) NHSBT's objective to move toward a more donor-friendly way of haemoglobin testing, that can improve donor's experience and optimise donor session flow.

Our power calculation is based on having 80% power to detect a 10% relative difference in false pass rate between the current NHSBT screening method and either: (i) Hemocue® on capillary blood; (ii) a "post-donation" screening strategy, or (iii) a non-invasive strategy to measure pre-donation haemoglobin concentration. The sample size calculations are based on a direct (ie, within person) comparison using a McNemar's paired test. Using information on a previous study and on INTERVAL data, we assumed a prevalence of "true" low haemoglobin of 10%, a sensitivity of the current NHSBT screening method of 55%, and a correlation coefficient between current method and any alternative novel strategies of 0.70 (**Figure 3**). Similar sample size will be required for the indirect (ie, between person) comparison of non-invasive devices (MBR Haemospect® vs Orsense NBM 200®), assuming that the sensitivity of non-invasive devices is about 20% (as reported by previous publications).

Figure 3. Sample size required for a within-person pairwise comparison to detect relative differences in false pass rate for low haemoglobin between screening strategies with 80% power

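### The primary non-invasive comparison treats two different devices as one method, so neither device is tested on its own against current practice

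*Protocol*

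**What the plan says.** Section 4.3.1 makes the principal assessment a comparison of the current NHSBT method with each of three "alternative methods (ie, three pair-wise comparisons"). Section 4.1 defines the third of these: "This method involves either of two hand-held spectrometer devices". It then describes one device as reflection spectroscopy and the other as occlusion spectroscopy, from different manufacturers.

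Section 4.2 describes Stage 1 as a "head-to-head comparison in a common set of about 12,500 participants" and says that each donor at visit 2 receives "one of the two non-invasive tests (ie, either MBR Haemospect® or Orsense NBM200"). Section 9.2.3 settles which one: "whichever is in current use by the mobile team". Table 2 in Section 8 has a single row, "Non-invasive (one of two"), marked for Stage 1 visit 2 and for Stage 2.

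Section 16.1 powers the third comparison for "a non-invasive strategy to measure pre-donation haemoglobin concentration", again as one entry. Section 16.2 says that comparisons with the current method are within person and that the two devices are compared between persons. Section 4.3.2 lists device against device as secondary endpoint 2, and Section 4.2 gives that question a second stage of about 13,000 donors, with over-sampling of non-European ancestry. No section sets a primary comparison of each device with the current method, or a sample size for one.

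**The concern.** The study is meant to tell a blood service which method to use, and Section 4.2 itself treats the non-invasive strategy as a choice between two products. A false pass rate averaged over both belongs to neither. Its weights are the shares of donors who met each device, which follow team use and are not fixed in the protocol. Another mix would give another primary result from the same two devices.

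Two things are at stake. If one device is better than current practice and the other worse, the primary comparison can show no difference. And if the result is later read per device, the stated power belongs to the pooled sample of about 12,500, not to the part of it measured by one device.

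**Working it through.** **1. Does the text imply pooling?** Three comparisons, a common set of about 12,500 for all of them, and one device per donor fit together only if both devices count as one method. With two non-invasive methods there would be four comparisons, and neither device would cover the common set.

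**2. Can pooling mislead?** False pass rate = prevalence × (1 − sensitivity). Section 16.1 assumes prevalence 10% and current sensitivity 55%. The device sensitivities and the 1:1 split below are illustrative.

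- Current method: 0.10 × 0.45 = 4.5%
- Device with 45% sensitivity: 0.10 × 0.55 = 5.5%
- Device with 65% sensitivity: 0.10 × 0.35 = 3.5%
- Pooled 1:1: (5.5% + 3.5%) / 2 = 4.5%

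The pooled difference from the current method is zero, although one device is worse by one percentage point and the other better by one.

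**3. The protocol's sample size.** Inputs from Section 16.1: McNemar test, 80% power, 10% relative difference, correlation 0.70. Alpha is not stated, nor whether the correlation applies to all donors or only to those with low haemoglobin. With p1 and p2 the two false pass rates:

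- p11 = p1·p2 + 0.70·√[p1(1−p1)·p2(1−p2)]
- discordant total pd = p1 + p2 − 2·p11, and d = |p1 − p2|
- n = [z(1−α/2)·√pd + z(0.80)·√(pd − d²)]² / d²

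All donors: p1 = 0.045, p2 = 0.0405, so pd = 0.01457 + 0.01007 = 0.02464 and d = 0.0045. Low-haemoglobin donors: 0.45 and 0.405, so pd = 0.09680 + 0.05180 = 0.14860 and d = 0.045; n is then divided by 0.10.

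| Scale | Two-sided α 0.05 | Two-sided α 0.05/3 |
|---|---|---|
| All donors | 9,549 | 12,738 |
| Low haemoglobin | 5,736 | 7,655 |

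Of these, the all-donor scale with alpha split over three comes within 2% of 12,500 (power 79% at 12,500). Enrolment agrees with it: 18,000 × 0.70 = 12,600.

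**4. Power for one device.** Power = Φ{[d·√n − z(1−α/2)·√pd] / √(pd − d²)}, with n multiplied by 0.10 on the low-haemoglobin scale. Assuming a 1:1 split in both stages, Stage 1 gives 12,500 / 2 = 6,250 per device, and Stage 2 adds 13,000 / 2 = 6,500, making 12,750.

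| Donors per device | Scale | α 0.05 | α 0.05/3 | α 0.05/4 |
|---|---|---|---|---|
| 6,250 (Stage 1) | All donors | 62% | 45% | – |
| 6,250 (Stage 1) | Low haemoglobin | 83% | 70% | – |
| 12,750 (both stages) | All donors | 90% | 80% | 77% |
| 12,750 (both stages) | Low haemoglobin | 99% | 96% | 95% |

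**5. At the protocol's own expectation.** Section 16.1 expects device sensitivity of about 20%. The false pass rate is then 0.10 × 0.80 = 8.0% against 4.5%. With 6,250 donors, power is near 100%, even with zero correlation and alpha 0.05/3.

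**6. Are the data there?** Table 2 and Sections 10.3 and 10.4 give each Stage 2 donor the current method, one device and the sample for the analyser. That is the same within-person set as at Stage 1 visit 2.

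**The case against.** The strongest reply is that no sentence says that the two devices' data will be combined. The authors know that a device must be chosen, and a separate analysis plan could run the third comparison per device. It is true that pooling is inferred. But the number of primary comparisons and the definition of the third method stand in the protocol and in its power statement; an analysis plan that used four would depart from both.

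Second, device against device is a pre-specified endpoint with its own stage, so a difference between devices should be seen. That stands as far as it goes. For false pass rates of 9% and 7%, about 6,500 donors per device give roughly 99% power (unpaired, two-sided 0.05). In that case both rates are far above 4.5%, so pooling would not change the conclusion against current practice either. Pooling does harm when the devices lie on either side of the current method, as in the 45% and 65% example. A between-device contrast does not say whether either device beats current practice, which is the primary question.

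Third, a reader might infer that the study is underpowered for each device. The documents do not support that. The 1:1 split and alpha are assumptions, one reading stays above 80% in Stage 1 alone, and at the expected 20% sensitivity power is not an issue. Nor does the protocol exclude Stage 2 from the primary comparison: it says that Stage 2 focuses on the devices, and Section 4.3.1 speaks of donors in the study.

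**Conclusion.** The point holds as a defect in how the primary comparison is defined. As written, the non-invasive result is an average over two devices with uncontrolled weights. It describes no adoptable method, and at the protocol's prevalence it can show exactly no difference while the two devices lie one percentage point on either side of current practice. This rests on reading three comparisons and the common set of about 12,500 together; the protocol does not announce pooling outright.

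The loss of power is secondary and conditional. It applies to the stated 10% relative difference and assumes an even split, which the protocol does not give. An uneven split would leave the less-used device with fewer than 6,250 Stage 1 donors.

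**What to change.** In Sections 4.3.1, 16.1 and 16.2, define the non-invasive primary comparison as each device separately against the current method, within person. Use Stage 1 visit 2 and Stage 2 data, stratified by stage because Stage 2 over-samples donors of non-European ancestry, and show Stage 1 alone beside it. Restate sample size and power per device, with alpha, the scale of the correlation and the expected device split written down.

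The cost is wording, one more primary comparison (four instead of three) and slightly more analysis. No new data are needed. Splitting alpha over four is optional; it would put per-device power at 77% to 95% with both stages.
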